7.4 Study Assessments

The following table provides the Schedule of Evaluations used in the study:

7.5 Schedule of Activities (Aims 1 and 3)

Table 2:

| | Pre-Visit Contact ¹ | Baseline | 12 Months ³ |
|---|---|--|-------------------------------------|
| Contact (C)/ Visit (V)/Medical Record Review (MRR) | C1 | V1 | C2/MRR⁵ |
| Time point, days (Visit window) | Prior to outpatient visit (≤ -1) | Within 30 days of pre-visit contact | 365 ± 30 (C2) |
| Contact patient re: interest in study visit ¹ | X | | |
| Informed consent | | X | |
| Demographics | | X | |
| Medical history (Co-morbidities) ² | | X | |
| Vaccination status | | X | X |
| CAPTURE 5-item questionnaire | | X | X |
| CAPTURE item additional questionnaire | | X | |
| Peak Expiratory Flow (PEF) | | X | |
| Height and weight | | X | |
| Respiratory medications review | | X | X |
| Spirometry ⁴ | | X* | |
| Respiratory symptoms, exacerbation assessment | | X | X |
| Smoking exposure history | | X | |
| Smoking cessation review ⁶ | | | X |
| COPD Assessment Test (CAT) | | X | X |
| Adverse Events | | X | |
| Medical record review | | | X |

1. Optional per site recruitment preferences
2. Comorbidities including cardiovascular, respiratory and malignant disorders
3. Recorded for a subset of participants who meet any of the following criteria: 1) CAPTURE+ subjects defined as CAPTURE Score ≥ 5 or CAPTURE score of 2, 3, or 4 with a low PEF, defined as <350 L/min for males and <250 L/min for females 2) abnormal spirometry defined as post-bronchodilator $FEV_1/FVC < 0.70$ or $FEV_1 < 80\%$ predicted at baseline, or pre-bronchodilator $FEV_1/FVC < 0.65$ or $FEV_1 < 70\%$ predicted for patients who do not complete post-bronchodilator spirometry; and, 3) a random sample of approximately 5% of those who do not meet criteria 1 and 2. For participants meeting criteria 1 and 2 who cannot or choose not to complete the 12-month assessment, medical record review will still be completed. For participants meeting criteria 1 and 2 who change medical practices and medical record review cannot be completed, patients will be contacted for completion of patient reported data. For participants meeting criterion 3 where all of the protocol-specified 12-month assessments cannot be made, another participant will be selected at random to replace this participant.
4. Pre-bronchodilator spirometry will be done for all participants. Post-bronchodilator spirometry will be performed for participants with abnormal spirometry ($FEV_1/FVC < 0.70$ or $FEV_1 < 80\%$ predicted) *If the participant has taken a bronchodilator within a 2-hour window of spirometry the spirometry will be considered post-bronchodilator and a pre-bronchodilator spirometry will not be done.
5. The 12-month assessment consists of patient reported data, collected by the COPD Foundation, and medical record review completed by site coordinators.
6. This will be completed in those that are smoking at V1.

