The CAPTURE Study: Validating a unique COPD case finding tool in primary care

Protocol Number: 1R01HL136682

National Clinical Trial (NCT) Identified Number:

NCT03581227, NCT03653611, NCT03583099

Principal Investigators:

[name]., Weill Cornell Medicine

[name]., University of Michigan

Funder:

National Heart, Lung, and Blood Institute (NHLBI)

Version Number: v. 8.0

17 July 2023

| Protocol Amendment 8.0 - Summary of Changes | | | | |
|---|-------------|----------------|--|--|
| Location | Page Number | Type of Change | Description | Rationale |
| Cover page | --- | Administrative | Update Protocol Version to 8.0 and update version date to 17JUL2023 | Amendment version and date |
| 1.1 Synopsis | 7 | Clarification | 
Secondary Endpoints
 
 • Aim 3 – O All of the above endpoints for Aim 3, in the population of participants defined by each of the following instead of CAPTURE+ status: 1) clinically significant COPD, 2) spirometric COPD, 3) Mild COPD 4) preserved ratio, impaired spirometry (PRISM), and 5) symptomatic non-obstructed (SNO) | Clarification of the secondary endpoints and what participants will be analyzed. |
| 1.3 Schedule of Assessments | 11,12 | Edit | 
Footnote 3:
 
3. Recorded for a subset of participants who meet any of the following criteria: 1) CAPTURE+ subjects defined as CAPTURE Score > 5 or CAPTURE score of 2, 3, or 4 with a low PEF, defined as <350 L/min for males and <250 L/min for females 2) abnormal spirometry defined as post-bronchodilator FEV1/FVC < 0.70 or FEV1 < 80% predicted at baseline, or pre-bronchodilator FEV1/FVC < 0.65 or FEV1 < 70% predicted for patients who do not complete post-bronchodilator spirometry; and, 3) a random sample of approximately 5% of those who do not meet criteria 1 and 2. For participants meeting criteria 1 and 2 who cannot or choose not to complete the 12-month assessment, medical record review will still be completed. For participants meeting criteria 1 and 2 who change medical practices and medical record review cannot be completed, patients will be contacted for completion of patient reported data. For participants meeting criterion 3 where all of the protocol specified 12-month assessments cannot be made, another participant will be selected at random to replace this participant.
 | The footnotes were edited to delete comment on replacing control patients who did not have availability of follow up data. |

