1.3 SCHEDULE OF ACTIVITIES (SOA)

Table 1: Schedule of Activities (Aims 1 and 3)

| | Pre-Visit Contact ¹ | Baseline | 12 Months ³ |
|--|---|-------------------------------------|------------------------|
| Contact (C)/ Visit (V)/Medical Record Review (MRR) | C1 | V1 | C2/MRR ⁵ |
| Time point, days (Visit window) | Prior to outpatient visit (≤ -1) | Within 30 days of pre-visit contact | 365 \pm 30 (C2) |
| Contact patient re: interest in study visit ¹ | X | | |
| Informed consent | | X | |
| Demographics | | X | |
| Medical history (Co-morbidities) ² | | X | |
| Vaccination status | | X | X |
| CAPTURE 5-item questionnaire | | X | X |
| CAPTURE item additional questionnaire | | X | X |
| Peak Expiratory Flow (PEF) | | X | |
| Height and weight | | X | |
| Respiratory medications review | | X | X |
| Spirometry ⁴ | | X* | |
| Respiratory symptoms, exacerbation assessment | | X | X |
| Smoking exposure history | | X | |
| Smoking cessation review ⁶ | | | X |
| COPD Assessment Test (CAT) | | X | X |
| COVID-19 Questionnaire | | X | X |
| Adverse Events | | X | |
| Medical record review Additional COVID-19 items | | | X X |

1. Optional per site recruitment preferences
2. Comorbidities including cardiovascular, respiratory and malignant disorders
3. Recorded for a subset of participants who meet any of the following criteria: 1) CAPTURE+ subjects defined as CAPTURE Score ≥ 5 or CAPTURE score of 2, 3, or 4 with a low PEF, defined as <350 L/min for males and <250 L/min for females 2) abnormal spirometry defined as post-bronchodilator FEV₁/FVC < 0.70 or FEV₁ $< 80\%$ predicted at baseline, or pre-bronchodilator FEV₁/FVC < 0.65 or FEV₁ $< 70\%$ predicted for patients who do not complete post-bronchodilator spirometry; and, 3) a random sample of approximately 5% of those who do not meet criteria 1 and 2. For participants meeting criteria 1 and 2 who cannot or choose not to complete the 12-month assessment, medical record review will still be completed. For participants meeting criteria 1 and 2 who

change medical practices and medical record review cannot be completed, patients will be contacted for completion of patient reported data.

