4.1 Preface

This Statistical Analysis Plan (SAP) describes statistical methods and analyses for the CAPTURE (COPD Assessment in Primary Care To Identify Undiagnosed Respiratory Disease and Exacerbation Risk) study, with emphasis on methods and analyses for the clinical trial component (Aim 3) of the CAPTURE Study Protocol version 7.0, dated June 25, 2023. This document should be read in tandem with the CAPTURE Study Protocol. When mentioned, CAPTURE Study Protocol Aim 1 and Aim 2 goals and analyses are grayed out in this document because they are out of scope of this SAP.

Chronic obstructive pulmonary disease (COPD) is the fourth leading cause of death in the US and a major cause of morbidity, mortality and health care expenditures. In primary care settings, the primary contact point for individuals seeking health care, COPD is often under diagnosed and associated opportunities for correct disease management are missed. The CAPTURE tool was developed to identify individuals

with undiagnosed COPD, and preliminary data has shown high sensitivity and specificity towards this goal. However, its use in primary care settings, where its potential impact on improved health care utilization is high, has not yet been studied.

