| Preserved ratio, impaired spirometry (PRISm) | Participants without spirometrically defined COPD who have post-bronchodilator $FEV_1 < 80\%$ predicted. Among participants who do not complete post-bronchodilator spirometry and have pre-bronchodilator $FEV_1/FVC \geq 0.7$, those with $FEV_1 \geq 80\%$ predicted will be considered not to have PRISm and those with $FEV_1 < 80\%$ predicted will be considered to have undetermined PRISm status in primary analyses. |
| Symptomatic non-obstructed (SNO) | Participants without spirometrically defined COPD and without PRISm who have a COPD Assessment Test score ≥ 10 . |

Longitudinal Follow-up

A pre-defined subgroup of enrolled participants, who meet any of the below criteria, will undergo longitudinal follow-up at 12 months:

1. CAPTURE+ participants, as defined above.
2. Participants who have spirometrically defined COPD, as defined above, or post-bronchodilator $FEV_1 < 80\%$ predicted at baseline. If post-bronchodilator spirometry is not completed, then pre-bronchodilator $FEV_1 < 70\%$ predicted will be considered to satisfy this criterion for follow-up.
3. A random sample of approximately 5% who do not meet criteria 1 – 2.

Participants who meet the criteria for follow-up will be sent notification/reminder letters within the first three weeks of enrollment and at three, six, and nine months. Patient-reported data will be collected by COPD Foundation via telephone, secure web-based server, or mail-based methodologies, based on participant preference.

Subject medical data will be collected from the medical record to assess for changes in practice-level care.

[figure not shown]

Figure 1

The hypothesis for Aim 3 is that sites where COPD and CAPTURE education and patient-level CAPTURE data are provided to clinicians will exhibit improved COPD diagnosis and COPD-related care compared to sites where COPD education is provided to clinicians.

7 Inclusion-Exclusion Criteria and General Study Population for Aim 3

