Multiple imputation of missing values in the baseline and 12-month follow-up data will be used to create 20 complete data sets. The set of patients included in each data set will be all of those selected for 12-month follow-up. The imputation method will be multivariate imputation by chained equations (MICE)⁶ as implemented in the R package 'mice'⁷.

Missing values of baseline spirometry FVC % predicted and FEV₁ % predicted will be imputed using linear regression models with the following predictors: age, gender, height, race, education, BMI, CAT score, asthma history, short-acting bronchodilator use, maintenance respiratory medication, and any follow-up outcomes for which baseline spirometry measurements will serve as predictors (selection of those predictors is described below). Predicted FVC and FEV₁ volumes will be calculated from the NHANES reference equations, allowing for calculation of the FVC, FEV₁, and FEV₁/FVC corresponding to the imputed % predicted values as needed.

For the purpose of organizing the imputation procedures, the 12-month follow-up outcomes will be grouped as follows:

- Pulmonary care outcomes:
 - Spirometry referral/completion
 - New diagnosis of COPD
 - New prescription for respiratory medication
 - Referral to pulmonologist or other respiratory specialist
 - Pulmonary rehab referral/completion
- Flu vaccination:
 - Flu shot recommended/ordered/administered
- Smoker-specific outcomes:
 - Counseling/recommendation for smoking cessation
 - Smoking cessation program referral/completion
 - New prescription for smoking cessation medication
 - Referral to a smoking quit line

Missing values of follow-up outcome variables, all of which will be binary (yes or no), will be imputed

using logistic regression models. For each outcome variable, the predictors will include, minimally, the following:

- All other variables from the medical record review and follow-up survey within the same group of outcomes. That is, medical record review data will be used to impute missing follow-up survey data, and follow-up survey data will be used to impute missing medical record data.
- Intervention group interacting with CAPTURE status. Intervention group must be included to avoid bias when using the imputed data to estimate the intervention effect. Interaction with CAPTURE status is included because the intervention effect is hypothesized to depend on the different recommendations associated with being classified as CAPTURE+ vs CAPTURE-.

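### SAP 7.5 footnote 3 keeps a rule for replacing random-sample participants that Protocol v8.0 does not contain, and leaves open whether replaced participants still count as selected for follow-up

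*SAP*

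**What the plan says.** Both documents follow three groups to 12 months: CAPTURE+ participants (criterion 1), those with abnormal baseline spirometry (criterion 2), and a random sample of the rest (criterion 3).

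- **SAP 7.5, footnote 3.** Participants under criteria 1 and 2 stay in whatever happens at 12 months: the chart is reviewed if they do not complete the assessment, and they are surveyed if the chart cannot be reached. For criterion 3, when the assessments cannot be made, "another participant will be selected at random to replace this participant".
- **Protocol v8.0, section 1.3, footnote 3.** It has the same three criteria and the same two provisions for criteria 1 and 2. It ends with participants who "change medical practices and medical record review cannot be completed, patients will be contacted for completion of patient reported data". Nothing on replacement follows.
- **Protocol v8.0, summary of changes.** The stated reason is: "The footnotes were edited to delete comment on replacing control patients who did not have availability of follow up data".
- **SAP 4.1.** The SAP is written against "CAPTURE Study Protocol version 7.0, dated June 25, 2023". The current protocol is v8.0 of 17 July 2023.
- **SAP 6.1.** The third follow-up group is "A random sample of approximately 5% who do not meet criteria 1 – 2", with no replacement rule.
- **SAP 9.5.** The main analysis of primary and secondary endpoints uses complete follow-up only. For multiple imputation, "The set of patients included in each data set will be all of those selected for 12-month follow-up".

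**The concern.** A random sample is useful because membership is fixed before the outcome, or its absence, is known. Replacing a member because 12-month data could not be obtained makes membership depend on a post-baseline event. Criteria 1 and 2 have no such rule, so one cohort has two retention rules.

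The SAP does not say whether a replaced participant remains in the set selected for follow-up. If not, that person's missing data vanish from analyses meant to show how much missing data matter: the negative and positive single imputations, the multiple imputation, the comparison of patients with and without complete follow-up, and the disposition counts. The SNO, No COPD and CAPTURE- results could then look more complete than the follow-up really was.

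**Working it through.** **1. The texts compared.** The two footnotes match up to the change-of-practice provision; the SAP then adds the criterion-3 sentence. This is a conflict between two current texts. The summary of changes only confirms that the deletion was deliberate. SAP 6.1 defines the sample without replacement, and SAP 14.1 does not list replacement as a departure from the protocol. The SAP's reference to v7.0 makes a missed update the likely cause.

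**2. What the rule can reach.** SAP 11.1 restricts the primary analysis to CAPTURE+ participants, so no criterion-3 participant enters it. The power table contains no random-sample quantity either. With effective n per arm = 44 × 5 / (1 + 4 × ICC) and a two-sided 5% test against a 5% control rate, power at ICC 0.05, 0.10 and 0.15 is:

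| Improvement | Recomputed | Stated |
|---|---|---|
| +7.5% | 0.72, 0.65, 0.60 | 0.72, 0.65, 0.59 |
| +10% | 0.89, 0.84, 0.79 | 0.89, 0.84, 0.79 |

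The table reproduces and would not change. Criterion-3 participants can appear only in the CAPTURE-, No COPD and SNO populations, and they are only part of each. CAPTURE- also holds criterion-2 patients, and SNO and No COPD also hold CAPTURE+ patients.

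**3. Available figure on non-completion.** SAP 13.1, Table 9, gives the survey status on 25 March 2020 for everyone then eligible, not for the random sample:

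- completed: 248/380 = 65.3%
- lost to follow-up: 20/380 = 5.3%
- neither: 380 − 248 − 20 = 112

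Final non-completion in that group could lie anywhere from 5.3% (all 112 later respond) to (20 + 112)/380 = 34.7% (none do). Applying this range, called m, to criterion 3 is an assumption.

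**4. Effect on the single-imputation bounds.** Among patients with chart data, the all-positive rate minus the all-negative rate is at most the fraction with a missing survey, and less where the chart already shows the event. For the criterion-3 part as drawn, the gap is therefore at most m, about 5 to 35 points. If every non-responder were replaced by a responder and dropped, the gap would be 0. In a whole population the lost width is at most w × m, where w is the criterion-3 share. The documents do not give w.

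**5. Shift in a rate (illustration).** Completer rate minus rate in the sample as drawn = m × d, where d is the completer minus non-completer difference. With d assumed at 5 to 15 points:

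- m = 0.35: 0.35 × 5 = 1.75 to 0.35 × 15 = 5.25 points
- m = 0.053: 0.053 × 5 = 0.3 to 0.053 × 15 = 0.8 points

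This applies to the criterion-3 part only. A complete-case analysis conditions on completion with or without the rule, so deleting the sentence does not remove this shift there. It matters where the sample as drawn is the target, as in the multiple imputation.

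**The case against.** The strongest reply is that this is version lag in a schedule footnote with little analytic reach. Much of that stands.

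- **Comparability.** A reader might infer that random-sample results would describe completers while CAPTURE+ results would not. The documents do not support this. SAP 9.5 makes the main analysis complete-case for every population, and SAP 11.1 and 11.2 compare arms within a population, not CAPTURE- with CAPTURE+.
- **Completers only.** A reader might infer that draws repeat until a completer is found. The SAP does not say so: the replacement is itself a random draw and may also fail to respond. The condition in "For participants meeting criterion 3 where all of the protocol-specified 12-month assessments cannot be made, another participant will be selected at random to replace this" can also mean that no assessment could be made, in which case partial completers stay.
- **Share replaced.** A reader might take one minus the 65% survey figure and conclude that about 35% of the draw would be replaced. That figure is an interim count across all eligible patients, with only 20 of 380 lost. Reaching 35% also requires every survey non-response to trigger a replacement.
- **Imputation set.** A replaced person was still selected at some point, and SAP 9.5 frames its missing-data comparison around prospective selection. This leans towards keeping the original draw, but the SAP never says so.

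What the reply does not remove is an explicit rule in a current document, absent from the current protocol, that acts on a post-baseline event. The silence on who remains selected is where it can reach the results.

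**Conclusion.** The conflict is certain from the texts. Its consequence is conditional and minor. The primary endpoint and its power are untouched, and the complete-case secondary analyses are little affected.

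If replaced participants are dropped, the criterion-3 part of CAPTURE-, No COPD and SNO is selected on follow-up availability. Missingness can then be understated in the two single-imputation analyses, the multiple-imputation set, the comparison of complete with incomplete follow-up, and the CONSORT counts.

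The size of any bias cannot be estimated. The documents do not give the number of criterion-3 participants, their completion rate, how many replacements occurred, or how non-completers differ. The figures in steps 3 to 5 show scale under stated assumptions and are not predictions. Nothing in the documents suggests that replacement would act differently in the two arms.

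**What to change.** 1. Delete the replacement sentence from SAP 7.5 footnote 3 and update the SAP's protocol reference to v8.0.
2. State that every criterion-3 participant originally drawn remains selected for follow-up, with missing data handled as in SAP 9.5.
3. Flag any replacements already made and report their number by arm. This record is needed because SAP 9.5 shows that, by 21 March 2023, sites holding about 84% of selected patients had finished follow-up, before v8.0 existed.
4. Show the imputation analyses of CAPTURE-, No COPD and SNO with and without the replacements. Excluding replacements outright would be a preference; showing both is enough.

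The cost is a wording change, one data flag, a small amount of extra analysis and slightly fewer complete random-sample participants. SAP 9.2 requires decisions to be documented before unblinding and database lock, so the rule should be written by then.

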7.6 Baseline Assessments and Data Collection

CAPTURE Questionnaire: Participants will complete the five-item self-administered questionnaire. The questionnaire will be scored on a scale of 0-6, with higher scores indicating a higher likelihood of COPD diagnosis. The score calculated and recorded by study site personnel will be used in all primary analyses, regardless of whether the score agrees with the individual CAPTURE questionnaire responses, since the study site personnel's CAPTURE scoring represents the information conveyed to clinical providers.

Peak Expiratory Flow (PEF): PEF will be measured for all participants in L/min, with a quality assurance range of 100-1000 L/min. The participant will perform three PEF tests. All three measurements will be recorded, and the largest of the measurements will be used in the CAPTURE Tool. The study site personnel's indication on the scored CAPTURE form about whether the maximum PEF falls below the predetermined threshold of <350L/min (males) or <250L/min (females) will be used to define CAPTURE+ participants in all primary analyses, regardless of whether that indication agrees with the individually recorded PEF values.

Spirometry: Spirometry will be performed for measurement of forced vital capacity (FVC), forced expiratory volume in one-second (FEV₁), and calculation of FEV₁/FVC. FEV₁ and FVC are measured in liters and have expected ranges of 0.4-8.0 liters. FEV₁ values less than 30% of the predicted values will be adjudicated by the study chair.

NHANES prediction equations, which are programmed into the Easy On PC spirometers, will be used to calculate the predicted lung function levels. These require the input of age, height, race, and sex. For people of mixed or unknown race the White prediction equations will be used.

Adjudication of the Presence of Obstruction on Post-Bronchodilator Spirometry: The presence of obstruction is determined by the presence of an FEV₁/FVC ratio less than 0.70 after the administration of a bronchodilator. A bronchodilator will be administered to study subjects whose baseline FEV₁/FVC is less than 0.70 or whose FEV₁ is less than 80% of the predicted value.

If a subject is unable to complete a post-bronchodilator spirometry (refusal, technical error on the part of coordinator, etc.), and the pre-bronchodilator FEV₁/FVC is less than 0.65, the patient will be considered to have COPD for the purpose of follow-up in this study.

Height and Weight: Height and weight will be recorded in order to determine appropriate prediction equations for spirometry and possible effect of obesity on spirometry. Height will be recorded in inches, and weight will be measured in pounds.

Demographic Data Collection: Demographic data including date of birth, gender, ethnicity, race, educational level, current employment status, living arrangement and health insurance will be entered into the EDC system.

Medical History: Previous medical diagnoses will include comorbidities such as cardiovascular, respiratory, and malignant disorders. Influenza vaccination history will also be recorded.

Statistical Analysis Plan

CAPTURE

Concomitant Medication Review: Respiratory medications will be recorded at baseline for all participants.

CAPTURE Additional Items Questionnaire: Participants will complete the 13 item self-administered questionnaire.

COPD Assessment Test (CAT): Participants will complete the eight item self-administered questionnaire. Each item is on a scale of 0-5 with higher scores indicating worse health status.

Respiratory Symptoms, Smoke Exposure and Exacerbation-Like Events: History of respiratory symptoms and exacerbation like events over the past year as well as smoke exposure (including e-cigarette or equivalent) will be recorded.

Adverse Events: Adverse events related to study procedures will be recorded by the coordinator.

Practice Characteristics: The locations of participating clinical practices will be categorized based on designation as rural by the Federal Office of Rural Health Policy (FORHP) / Health Resources & Services Administration (HRSA). A practice location will be classified as rural if the ZIP code appears in the Eligible ZIP Codes file downloadable from the FORHP website: <https://www.hrsa.gov/rural-health/about-us/definition/datafiles.html>. Other data describing the characteristics of participating practices will be collected from study site personnel.

6.6.2: Longitudinal follow-up

Follow-up efficacy assessments are collected from the time of baseline to 12 months in selected cohorts (as described in section 6.1).

Table 3: Data collected from medical records include:

| All participants undergoing 12-month follow-up as described in section 6.1 | Current Smokers Only |
|--|--|
| Clinical spirometry ordered or administered | Smoking cessation counseling |
| New recorded clinical diagnosis of COPD | New prescription for smoking cessation medication |
| New prescription for respiratory medication (long acting bronchodilator, inhaled steroids, oral anti-inflammatory) | Formal smoking cessation program referral/completion |
| Exacerbation like event assessment (hospital, ED, minute clinic, antibiotic/steroid prescription/administration) | Referral to a smoking quit line |
| Vaccination status | |
| Formal pulmonary rehabilitation program referral/completion | |

Statistical Analysis Plan

CAPTURE

| | |
|--|--|
| Data related to COVID-19 confirmed and suspected cases | |
|--|--|

Table 4: Data from clinical visits to be collected at follow-up by telephone, secure web-based server, or mail- based methodologies directly from participants and administered by COPD Foundation study personnel includes:

| All participants undergoing 12-month follow-up as described in section 6.1 | Current Smokers Only |
|--|--|
| Spirometry referral/completion | Referral to a smoking cessation program |
| New diagnosis of COPD | Referral to a smoking quit line |
| Referral to pulmonologist or other respiratory specialist | New prescription for smoking cessation medication |
| Exacerbation like event assessment | Over-the-counter patches/gum for smoking cessation |
| New prescription for respiratory medication (long acting bronchodilator, inhaled steroids, oral anti-inflammatory) | |
| CAT score | |
| Attendance of pulmonary rehabilitation | |
| COVID-19 related questions | |

